**OTHER SAFETY ANALYSES**

Not applicable.

**9.7.1.9 Other Analyses**

Not planned

**9.7.1.10 Extension Phase Analyses****DEFINITIONS OF ANALYSIS SETS IN EXTENSION PHASE**

The Safety Analysis Set of OLE-phase (SAS-OLE) is the subjects who received at least one dose of study drug and had at least one post dose safety assessment after starting OLE Phase.

The Efficacy Analysis Set of OLE-phase (FAS-OLE) is the group of subjects who received at least one dose of study drug and had at least one post-dose MMSE measurement after starting Open-label Phase.

**EFFICACY ANALYSIS**

For the efficacy endpoint, MMSE, descriptive statistics (median, mean, SD, minimum, maximum and number of patients with non-missing data) of the measurement and the change from week0 of extension phase to each visit will be presented by visit and total.

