#### 9.1.3 Open-label Extension (OLE) Phase

Before starting the OLE phase, subjects have to provide written informed consent to participate in OLE phase. Subjects, who have completed the DB phase, can be enrolled in the 24-week OLE phase. In this phase, treatment is initiated at 5 mg/day, and the dose is maintained until Week 6 (Day 28-42; for at least 4 weeks). After assessing clinical response at Week 6 visit, the dose can be increased to 10 mg/day. Dose reduction (from 10 mg/day to 5 mg/day) is permitted when the investigator judged it difficult to continue the 10 mg/day administration. It is possible to increase the dose to 10 mg/day again. Subjects will visit the study institution at Week 6, 12, and 24.

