#### 9.4.3 Method of Assigning Subjects to Treatment Groups

At the time of the Baseline visit, patients meeting the eligibility criteria will be randomly assigned (1:1) to either donepezil group or placebo group by IWRS system according to a computer-generated randomization code generated by an independent statistician.

The list of patient randomization codes will be generated using PROC PLAN in the SAS® procedures. A stratified block randomization approach will be used for the randomization with MMSE ( $\leq 19$ ,  $20 \leq$ ) as stratum in each study site.

(Open-label extension)

This is an open-label extension phase. Subjects, who have completed the DB phase and have consented to continue participation of the study, can be enrolled in the 24-week open-label extension phase. All subjects who provide signed informed consent to participate in this phase will be assigned to receive active drug. There is no randomization in this phase.

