### **9.7 STATISTICAL METHODS**

All statistical analyses will be performed by the sponsor or designee. Statistical analyses for DB phase will be performed after a snapshot of the database is obtained and released for unblinding.

Statistical analyses for OLE phase will be performed after the study is completed and the database is locked.

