### 9.7.1.4 Demographic and Other Baseline Characteristics

Demographic and other baseline characteristics for each analysis set will be summarized for each treatment group and total of treatment groups using descriptive statistics (e.g., mean, SD, median, minimum, maximum and frequency, proportion). Continuous demographic and baseline variables include age, weight etc. Categorical variables include sex, age group etc.

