#### **9.7.1.8 Safety Analyses**

The evaluation of safety parameters will be conducted on the SAS. The incidence rates for AEs by body system, preferred term, severity, and relationship to study mediation will be calculated. Individual vital signs will be descriptively summarized by treatment group and total of treatment groups and visit. Changes from Baseline to each individual post- baseline visit and to the final visit will be calculated. For clinical laboratory parameters, changes from Baseline to each visit, will be summarized. Shift tables depicting shifts in or out of the normal range, from Baseline to the final study visit, will also be provided.

ECG data will be categorized at Baseline, and results for each subject at the end of treatment will be compared to those at Baseline. Data on other medications used by subjects during the study will be collected and summarized by therapeutic class and generic components.

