## ADVERSE EVENTS

The AE verbatim descriptions (investigator terms from the CRF) will be classified into standardized medical terminology using the Medical Dictionary for Regulatory Activities (MedDRA). Adverse events will be coded to the MedDRA (Version 15 or higher) lower level term (LLT) closest to the verbatim term. The linked MedDRA preferred term (PT) and primary system organ class (SOC) are also captured in the database.

A treatment-emergent AE (TEAE) is defined as an AE that emerges during treatment, having been absent at pretreatment (Baseline) or

- Reemerges during treatment, having been present at pretreatment (Baseline) but stopped before treatment, or
- Worsens in severity during treatment relative to the pretreatment state, when the AE is continuous.

Only those AEs that were treatment emergent will be included in summary tables. All AEs, treatment emergent or otherwise, will be presented in subject data listings.

Treatment-emergent AEs (TEAEs) will be summarized by treatment group. The incidence of TEAEs will be reported as the number (percentage) of subjects with TEAEs by SOC and PT. A subject will be counted only once within a SOC and PT, even if the subject experienced more than one TEAE within a specific SOC and PT. The number (percentage) of subjects with TEAEs will also be summarized by maximum severity (mild, moderate, or severe).

The number (percentage) of subjects with TEAEs will also be summarized by relationship to study drug (possibly related, probably related, and not related).

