**SAFETY ANALYSIS**

The same analysis method like the double-blind phase will be presented by total.

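### The open-label extension tables pool former placebo and former donepezil subjects, so first exposure cannot be told apart from continued exposure

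*Protocol*

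**What the plan says.** Protocol section 9.7.1.10 defines one safety set and one efficacy set for the extension, neither divided by earlier treatment. For MMSE, the measured value and "the change from week0 of extension phase to each visit will be presented by visit and total". For safety, "The same analysis method like the double-blind phase will be presented by total". Section 9.7.1.9 plans no other analyses.

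The double-blind sections are worded differently. Baseline characteristics (9.7.1.4) "will be summarized for each treatment group and total of treatment groups using descriptive statistics". In 9.7.1.8, "Individual vital signs will be descriptively summarized by treatment group and total of treatment groups and visit", and under Adverse Events, "Treatment-emergent AEs (TEAEs) will be summarized by treatment group".

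On entry, section 9.1.3 admits subjects who completed the double-blind phase, without regard to arm. Section 9.4.3 adds: "All subjects who provide signed informed consent to participate in this phase will be assigned to receive active drug". The starting dose is common to all (9.1.3): "In this phase, treatment is initiated at 5 mg/day".

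**The concern.** The extension population is mixed by design. Former placebo subjects take donepezil for the first time. Former donepezil subjects have already had 24 weeks of it and begin the extension at the common starting dose, which is a step down for anyone on 10 mg/day at Week 24. A pooled MMSE change from extension Week 0 therefore averages the effect of starting the drug with the course of subjects who were already on it. Movements in opposite directions could cancel without showing.

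The safety tables have the same weakness. Former donepezil entrants are selected for having completed 24 weeks on drug, and former placebo entrants are not. Section 7.1.2 shows that this selection can matter: withdrawals for adverse events in Study 308 were 8.8% on placebo, 10.1% on 5 mg and 16.3% on 10 mg.

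What would be lost is the separate view of longer exposure. Subjects who took donepezil in both phases are the only ones in this trial with more than 24 weeks on drug, up to 24 + 24 = 48 weeks. The double-blind tables cannot show that period, and the extension tables as specified show it only mixed with new starters.

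**Working it through.** **1. Does the protocol fix pooling or leave it open?** Where both views are wanted, sections 9.7.1.4 and 9.7.1.8 name the treatment group and the total as separate items. Section 9.7.1.10 names only the total, over undivided analysis sets. The safety sentence even carries over the double-blind method but replaces the arm split with the total. Read against the protocol's own usage, this is a stated rule of presentation.

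**2. Is the baseline common?** Table 3 and section 9.5.2.2 make extension Week 0 the same visit as double-blind Week 24. At that visit one group has been on placebo and the other on donepezil for 24 weeks, so the change from Week 0 does not mean the same thing in the two groups.

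**3. Is the original arm known when the extension is analysed?** Section 9.7 states: "Statistical analyses for DB phase will be performed after a snapshot of the database is obtained and released for unblinding". The extension is analysed after study completion and database lock. The arm is therefore available.

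**4. How large could the masking be?** The plan has no figure of its own to reproduce, and the following is an illustration under assumptions.

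Formula: pooled rate = p × a + (1 − p) × b. Here p is the former-placebo share of the extension, a the rate in starters and b the rate in subjects already exposed.

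- p is assumed to be 0.4, 0.5 or 0.6. Randomization was 1:1, but completion and consent by arm are unknown.
- a is taken as the nausea rate on 5 mg, and b as the placebo rate of the same trial, both from section 7.1.3. The protocol gives no rate for previously exposed subjects.

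| Source | a | b | p = 0.4 | p = 0.5 | p = 0.6 | Shortfall against a |
|---|---|---|---|---|---|---|
| Study 319, 5 mg | 9.9% | 4.3% | 6.54% | 7.10% | 7.66% | 33.9%, 28.3%, 22.6% |
| Study 308, 5 mg | 11.1% | 7.8% | 9.12% | 9.45% | 9.78% | 17.8%, 14.9%, 11.9% |
| Study 308, 10 mg | 16.7% | 7.8% | 11.36% | 12.25% | 13.14% | 32.0%, 26.6%, 21.3% |

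First cell: 0.4 × 9.9 + 0.6 × 4.3 = 3.96 + 2.58 = 6.54, and (9.9 − 6.54)/9.9 = 33.9%. The 10 mg row is added because the extension allows 10 mg after its Week 6 visit.

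The shortfall is (1 − p)(a − b)/a. It is zero when b = a, so its size depends mainly on the assumed b.

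For MMSE the protocol gives no values. To show cancellation only, take arbitrary changes of +1 in former placebo and −1 in former donepezil subjects. The pooled mean is then −0.2, 0.0 or +0.2 at p = 0.4, 0.5 or 0.6.

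**The case against.** The best counter-argument is about weight. The objectives (section 8) and endpoints (9.7.1.1) are double-blind comparisons with placebo; the extension has no stated objective and no hypothesis. Adverse events on first exposure, and the MMSE effect, are already reported by arm in the randomized phase. In the extension everyone takes the same drug, so a total is a valid description of that population. All adverse events also go into subject listings, and columns by earlier treatment are often settled in the SAP or its table shells.

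Much of this stands. It limits the importance of the point, and the information is missing from the summary tables, not from the data. It does not remove the point, because section 9.7.1.10 states a presentation and does not defer it.

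The nausea percentages can also be challenged. The placebo rate is a chosen stand-in for previously exposed subjects, the rates come from randomized populations and not from consenting completers, and a different starter rate gives a different percentage. That is correct, and the figures should be read only as an illustration. That the two components cannot be recovered from a pooled table does not depend on them.

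A further objection is that a split among self-selected completers invites a comparison that randomization no longer protects. This stands as a reason to keep the columns descriptive.

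**Conclusion.** The concern holds. As written, the protocol pools two groups with different exposure histories and different kinds of baseline, and its extension tables cannot show which group drives an MMSE change or an adverse event rate. The size is unknown. Under the stated assumptions a pooled nausea rate would sit 12 to 34% below the starter rate using the 5 mg figures, and the gap would vanish if previously exposed subjects had the same rate as starters. No MMSE magnitude can be estimated from the protocol.

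The consequence is confined to how the extension is read. The co-primary, secondary and double-blind safety results are untouched. The change is worth making, but the trial's main conclusions do not depend on it.

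**What to change.** Amend section 9.7.1.10 so that extension MMSE and safety summaries are shown by original double-blind arm (placebo to donepezil, and donepezil to donepezil) as well as in total. For MMSE, give the value, the change from extension Week 0 and the change from double-blind baseline. The last item is not needed to separate the groups, but it gives both a common untreated reference point. State that the summaries are descriptive, with no test between the former arms.

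The cost is a wording change and extra table columns. It needs no new data, visits, subjects or alpha.

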**SAFETY ANALYSIS**

The same analysis method like the double-blind phase will be presented by total.

**9.7.2 Determination of Sample Size**

The primary endpoints are the change from baseline to Week 24 (LOCF) in ADAS-cog and the measurement at Week 24 (LOCF) of the CIBIC-plus.

The estimates of these endpoints were referred from the result of subgroup (MMSE less than 24) in pooled data of previous double blind studies (E2020-A001-307 and E2020-A001-308).

The mean difference and standard deviation of the change from baseline to final visit in ADAS-cog were estimated as  $-2.404 \pm 5.955$ , using pooled data of E2020 groups (5 mg+ 10 mg). When the significance level was set as 5.0% (two-tailed) and statistical power as 80.0%, the subject number needed to detect statistically significant difference by 2 sample t test was calculated to be 196 (98/arm).

On the other hand, the mean difference and the standard deviation of CIBIC-plus score at the final visit were estimated as  $-0.261 \pm 1.162$ , when CIBIC-plus was regarded as continuous measurement [scored from 1 (marked improvement) to 7 (marked worsening) point]. The subject number needed to reduce the probability that donepezil is inferior to placebo in point estimate to 2.5% or less, was calculated to be 308 (154/arm)..

Therefore, the subjects number required to achieve primary objectives simultaneously became 308 (154/arm). In consideration of exclusion from the analysis set (approximately 5%), the sample size was defined as 324 (162/arm).

### **9.7.3 Interim Analysis**

Not applicable

### **9.7.4 Other Statistical/Analytical Issues**

Not applicable

### **9.7.5 Procedure for Revising the Statistical Analysis Plan**

If the statistician determines that the analysis plan requires revision after the study begins, the person in charge of analysis and the study director will examine the validity of the revision and its influence on the objectives of the study, and determine if the revision can be implemented. The details of the revision will be described in the SAP and CSR for the study.

## **11 PROCEDURES AND INSTRUCTIONS (ADMINISTRATIVE PROCEDURES)**

### **11.1 CHANGES TO THE PROTOCOL**

Any change to the protocol requires a written protocol amendment or administrative change that must be approved by the sponsor before implementation. Amendments specifically affecting the safety of subjects, the scope of the investigation, or the scientific quality of the study require submission to health or regulatory authorities as well as additional approval by the applicable IRBs/IECs. These requirements should in no way prevent any immediate action from being taken by the investigator, or by the sponsor, in the interest of preserving the safety of all subjects included in the study. If the investigator determines that an immediate change to or deviation from the protocol is necessary for safety reasons to eliminate an immediate hazard to the subjects, the sponsor's medical monitor and the IRB/IEC for the site must be notified immediately. The sponsor must notify the health or regulatory authority as required per local regulations.

Protocol amendments that affect only administrative aspects of the study may not require submission to health or regulatory authority or the IRB/IEC, but the health or regulatory authority and IRB/IEC should be kept informed of such changes as required by local regulations. In these cases, the sponsor may be required to send a letter to the IRB/IEC and the Competent Authorities detailing such changes.

### **11.2 ADHERENCE TO THE PROTOCOL**

The investigator will conduct the study in strict accordance with the protocol (refer to ICH E6, Section 4.5 and KGCP).

### **11.3 MONITORING PROCEDURES**

The sponsor's/CRO's CRA will maintain contact with the investigator and designated staff by telephone, letter, or email between study visits. Monitoring visits to each site will be conducted by the assigned CRA as described in the monitoring plan. The investigator will allow the CRA to inspect the clinical, laboratory, and pharmacy facilities to assure compliance with GCP and local regulatory requirements. The CRFs and subject's corresponding original medical records (source documents) are to be fully available for review by the sponsor's representatives at regular intervals. These reviews verify adherence to study protocol and data accuracy in accordance with local regulations. All records at the site are subject to inspection by the local auditing agency and IRB/IEC review.

In accordance with ICH E6, Section 1.52, source documents include, but are not limited to the following:

- Clinic, office, or hospital charts
- Copies or transcribed health care provider notes which have been certified for accuracy after production

- Recorded data from automated instruments such as IxRS, x-rays, and other imaging reports, (e.g., sonograms, CT scans, magnetic resonance images, radioactive images, ECGs, rhythm strips, EEGs, polysomnographs, pulmonary function tests) regardless of how these images are stored, including microfiche and photographic negatives
- Pain, quality of life, or medical history questionnaires completed by subjects
- Records of telephone contacts
- Diaries or evaluation checklists
- Drug distribution and accountability logs maintained in pharmacies or by research personnel
- Laboratory results and other laboratory test outputs (e.g., urine pregnancy test result documentation and urine dip-sticks)
- Correspondence regarding a study subject's treatment between physicians or memoranda sent to the IRBs/IECs
- CRF components (e.g., questionnaires) that are completed directly by subjects and serve as their own source

#### **11.4 RECORDING OF DATA**

A CRF is required and must be completed for each subject by qualified and authorized personnel. All data on the CRF must reflect the corresponding source document, except when a section of the CRF itself is used as the source document. Any correction to entries made on the CRF must be documented in a valid audit trail where the correction is dated, the individual making the correct is identified, the reason for the change is stated, and the original data are not obscured. Only data required by the protocol for the purposes of the study should be collected. This study will use electronic CRF system. The investigator must sign by electronic signature on each CRF.

#### **11.5 IDENTIFICATION OF SOURCE DATA**

ICH GCP guidelines specifically acknowledge that data may in some cases be recorded directly on CRFs. According to ICH guidance, if sections of the CRF are to be considered source documents, these sections or pages should be identified in the protocol before study inception. All data to be recorded on the CRF must reflect the corresponding source documents. For the following item(s), the data recorded directly on the CRF are to be considered source data:

- (Using bullet format, add items to be recorded on the CRF that will be considered source data, e.g., reasons for discontinuation of study treatment, comments and other information on AEs [severity, relationship to study drug, outcome, etc.], reasons for dose modification, indication for prior/concomitant medication, sampling times for drug concentrations, sampling times for clinical laboratory tests.)

## **11.6 RETENTION OF RECORDS**

The circumstances of completion or termination of the study notwithstanding, the investigator is responsible for retaining all study documents, including but not limited to the protocol, copies of CRFs, the Investigator's Brochure, and regulatory agency registration documents (e.g., ICFs, and IRB/IEC correspondence). In addition, the sponsor will send a list of treatment codes by study subject to the investigator after the clinical database for this study has been locked. It is mandatory to keep the clinical related documents at least for 3 years from this clinical trial completion or termination.

It is requested that at the completion of the required retention period, or should the investigator retire or relocate, the investigator contact the sponsor, allowing the sponsor the option of permanently retaining the study records.

## **11.7 AUDITING PROCEDURES AND INSPECTION**

In addition to the routine monitoring procedures, the sponsor's Clinical Quality Assurance department conducts audits of clinical research activities in accordance with the sponsor's SOPs to evaluate compliance with the principles of ICH GCP and all applicable local regulations. If a government regulatory authority requests an inspection during the study or after its completion, the investigator must inform the sponsor immediately.

## **11.8 HANDLING OF STUDY DRUG**

All study drugs will be supplied to the principal investigator (or a designated pharmacist) by the sponsor. Drug supplies must be kept in an appropriate secure area (e.g., locked cabinet) and stored according to the conditions specified on the drug labels. The investigator (or a designated pharmacist) must maintain an accurate record of the shipment and dispensing of the study drug in a drug accountability ledger, a copy of which must be given to the sponsor at the end of the study. An accurate record of the date and amount of study drug dispensed to each subject must be available for inspection at any time. The CRA will visit the site and review these documents along with all other study conduct documents at appropriate intervals once study drug has been received by the site.

All drug supplies are to be used only for this study and not for any other purpose. The investigator (or site personnel) must not destroy any drug labels or any partly used or unused drug supply before approval to do so by the sponsor. At the conclusion of the study and as appropriate during the study, the investigator (or a designated pharmacist) will return all used and unused drug containers, drug labels, and a copy of the completed drug disposition form to the sponsor's CRA or, when approval is given by the sponsor, will destroy supplies and containers at the site.

## **11.9 PUBLICATION OF RESULTS**

All manuscripts, abstracts, or other modes of presentation arising from the results of the study must be reviewed and approved in writing by the sponsor in advance of submission pursuant to

the terms and conditions set forth in the executed Clinical Trial Agreement between the sponsor/CRO and the institution/investigator. The review is aimed at protecting the sponsor's proprietary information existing either at the date of the commencement of the study or generated during the study.

The detailed obligations regarding the publication of any data, material results, or other information, generated or created in relation to the study shall be set out in the agreement between each investigator and the sponsor or CRO, as appropriate.

